### **Participant Enrollment & Baseline Data Collection**

#### Pre-COVID Procedures

After data collectors completed the consent process, they measured the participant's blood pressure and then gathered data to verify eligibility and enroll eligible participants into the study. This data consists of gathering their height and weight, to verify eligibility by ensuring the participant's measured (as opposed to self-reported)-BMI is in the eligible range. If the participant's eligibility is confirmed additional data collection includes: waist circumference and a survey that the participant completed in RedCap.

#### COVID Procedures and Changes

1. An approved scale, automated blood pressure cuff, and tape measure for assessing waist circumference will be mailed to each site. Once the PAT staff member or data collector has dropped off the scale, blood pressure cuff, and tape measure or the mother is situated in the private room at the PAT site we will either:
  - a. Complete modified data collection via video call, in which we will i) see the participant stand on the scale; ii) use the automated blood pressure cuff; and iii) encircle her waist with the tape measure; these will be recorded entered live in REDCap.
  - b. If the participant is not able to complete a video call, she will complete the data collection by phone, and will receive instructions by the research team on (i) how to take a weight on the scale, (ii) take a photo of weight with her personal device (e.g., phone, ipad), (iii) remove their location tags, and (iv) send a photo of their ID number and weight on the scale, the reading on the blood pressure cuff, and the location on the tape measure to the research team which does not include any identifying factors (e.g. face, location, or name).

For all mothers, we will walk the participant through the process of setting up the scale, using the blood pressure cuff, and using the tape measure (e.g., locating the correct spot for assessing waist circumference). Further, we will utilize their self-reported height to calculate their BMI and ensure eligibility. Weight will be assessed first, as this is used to confirm eligibility. If the mother

is eligible, the remainder of the measures (blood pressure and waist circumference) will be completed.

2. The study team member will then conduct the RedCap Survey through the video call or over the phone.

Once the mother has completed data collection, the PAT staff member or data collector will collect the materials (i.e., scale, automated blood pressure cuff, and tape measure), sanitize them using the wipes provided by the research team, and stored local to the site. If the drop-off method is being used the pickup will ideally be coordinated with planned trips to the home to drop off PAT-related materials (e.g., handouts, materials for activities during personal visits/group connections) or personal visits.

### **Post Visit Data Collection**

#### Pre-COVID Procedures

Given the ongoing nature of the COVID-19 impacts, enrolled participants will be reaching their first post (12-month) and possibly second (24-month) data collection visit. Our current data collection procedures are similar to participant enrollment procedures. The data that is gathered in the post data collection visits include: weight, blood pressure, waist circumference and a survey in RedCap.

#### COVID Procedures and Changes

As Data Collectors are no longer able to travel to gather certain data points from the participant, the following changes will be needed to continue the post data collection process.

1. Using the same data collection materials as enrollment/baseline and the same procedure (i.e., Drop-off/ pick up method or Site method):
  - a. Complete modified data collection via the same procedures noted above for baseline (with the exception of self-reported height)
2. We will then conduct the RedCap Survey over the phone or video call.

For data collection at all time points, we will increase the amount of the participant incentive from \$20 to \$30, due to the increased time and effort on the part of the participant.

We recognize the dynamic nature of the pandemic situation. If a PAT staff member or data collector is not able to drop equipment off at the participant's house or the mother is not able to travel to the PAT site, we will revert to the procedures we used in the initial months of the pandemic (beginning in mid-March), which involved mailing a scale with instructions to the participant's home and scheduling a time for follow-up.

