### **M3 Appendix C.**

#### **HEALTH D&I (R01HL143360): Implications of COVID-19-Expanding for long-term data collection**

Our team initially put in place temporary methods to allow for recruitment/enrollment and follow-up data collection to occur during COVID-19. However, these were designed to be temporary, and therefore did not incorporate collection of important secondary outcomes (i.e., blood pressure, waist circumference). Expanding on the plans to resume recruitment, enrollment, and follow-up data collection of our study in the context of COVID-19 requires additional changes to the study components noted below.

- Screening and Consent
- Participant Enrollment & Baseline Data Collection
- Post Visit Data Collection
- Intervention delivery and tracking

Noting that this study takes place across 40 sites, each of which operates differently, we anticipate this as a starting place for sites currently prepared to implement these protocols. We propose the following modifications:

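### Appendix C's last-resort COVID procedure mails only a scale, so follow-up visits done that way lose waist circumference and blood pressure; adding a tape measure to the parcel would save waist at little cost

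*Combined protocol and SAP*

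**What the plan says.** Appendix C (M3) opens by explaining why the first COVID arrangements were replaced. They were stop-gaps that "did not incorporate collection of important secondary outcomes (i.e., blood pressure, waist circumference". They served enrolment as well as follow-up: "Our team initially put in place temporary methods to allow for recruitment/enrollment and follow-up data collection to occur during COVID-19".

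The replacement supplies a full kit: "An approved scale, automated blood pressure cuff, and tape measure for assessing waist circumference will be mailed to each site". The kit is taken to the mother's home or set up in a private room at the site. She then measures herself while coached by video, or by phone with photographs of the readings. The coaching explicitly covers "using the tape measure (e.g., locating the correct spot for assessing waist circumference".

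The follow-up section of the appendix lists what is due at 12 and 24 months: "weight, blood pressure, waist circumference and a survey in RedCap". It then adds a last resort for when neither delivery of the kit nor travel by the mother is possible. In that event the study goes back to its first pandemic arrangements, "which involved mailing a scale with instructions to the participant's home and scheduling a time for follow-up". No tape measure or cuff is named for that route.

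Table 1 (Schedule of Measurements, H2) puts waist circumference and blood pressure at baseline, 12 and 24 months. Statistical Methods (J3) analyses secondary continuous outcomes with the model used for weight change and reports changes from baseline. Its inclusion rule looks only at follow-up data and does not mention a missing baseline value.

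**The concern.** The fall-back brings back the gap that the appendix was written to close, and the fall-back sentence does not say so. A mother followed up this way gives a weight but neither waist nor blood pressure at that visit.

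Waist is worth protecting. In the earlier trial (Preliminary study, F1) it separated the arms at 12 months (p=0.04) and at 24 months (3.8 cm against -2.5 cm, p=0.005), whereas blood pressure did not differ. The rationale section (D1) also cites reduced waist circumference as part of the case for HEALTH.

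The loss also looks avoidable. Coached self-measurement of waist is already the standard COVID procedure, and the fall-back already sends a parcel.

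**Working it through.** **Step 1: the text.** Three statements in Appendix C, taken together, settle the follow-up loss.

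- The early methods did not collect waist or blood pressure (opening paragraph).
- The fall-back is those early methods (end of the follow-up section).
- Both measures are due at 12 and 24 months (follow-up section and Table 1).

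The loss is therefore stated by the plan and does not have to be guessed from the absence of a tape in the parcel.

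Baseline is less clear. The early methods covered enrolment, so any baseline taken with them lacks waist. But the fall-back sentence stands in the follow-up section, and the baseline section offers only drop-off or site measurement. The two cases differ as follows.

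| Visit done by mailed scale | Observed waist change lost |
|---|---|
| 12 months only | 12 months |
| 24 months only | 24 months |
| Baseline | 12 and 24 months |

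**Step 2: the plan's own figures.** The plan has no sample size for waist. Table 2 (J1) sizes weight only, with SD 10 kg, difference 4 kg, 19 sites per arm and two-sided 0.05. With n = 2[SD(z₀.₉₇₅ + z_power)/4]² and m = n(1 − ICC)/(19 − n·ICC), the required number per site is 5.39, 5.64 and 6.61 at power 0.8, and 7.35, 7.86 and 10.04 at power 0.9 (ICC 0.01, 0.02, 0.05). Rounded up, these are the tabulated 6, 6, 7 and 8, 8, 11. The 19 sites and 7 completers per site can therefore be carried over.

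**Step 3: illustration for waist.** Inputs:

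- 19 sites per arm and 7 completers per site (J1).
- ICC 0.05, the largest value in Table 2; its use for waist is an assumption.
- SD of 24-month waist change √[(10.6² + 9.1²)/2] = 9.88 cm, and difference 3.8 − (−2.5) = 6.3 cm (F1).
- Share f of completers without a waist change: assumed, because the plan gives no figure.

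If the loss is spread evenly over sites, m = 7(1 − f) and the design effect is DE = 1 + (m − 1)0.05. The standard error is 9.88√[2/(19m/DE)], and the difference detectable at 80% power is (1.960 + 0.842) × SE.

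| f | m | DE | m/DE | SE ratio | Detectable difference (cm) | Power for 6.3 cm |
|---|---|---|---|---|---|---|
| 0 | 7.0 | 1.300 | 5.385 | 1.00 | 3.87 | 0.995 |
| 10% | 6.3 | 1.265 | 4.980 | 1.04 | 4.02 | 0.992 |
| 20% | 5.6 | 1.230 | 4.553 | 1.09 | 4.21 | 0.987 |
| 30% | 4.9 | 1.195 | 4.100 | 1.15 | 4.43 | 0.978 |

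The SE ratio is √(5.385 ÷ m/DE); for f = 30%, √(5.385/4.100) = 1.146. If whole sites were lost instead, the ratio would be 1/√(1 − f), that is 1.05, 1.12 and 1.20.

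**The case against.** The best defence is that this is a disclosed contingency. The plan admits the limitation, builds a main COVID route that restores both measures, keeps the mailed scale for cases where that route fails, and expects further modifications (Additional challenges). Waist is not named in any of the Aim 1 hypotheses. Missing Outcome Data (J5) provides for mixed models, multiple imputation and sensitivity analyses. Under the assumptions above, power for the earlier 6.3 cm difference stays at 0.978 even with 30% loss. All of this stands, and it keeps the point small. It does not show that the values need to be lost, and J5 is generic: it says nothing about values missing because of the measurement route.

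Two stronger readings are tempting.

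- A reader might infer that the plan sends future baselines down the scale-only route, so that waist change cannot be derived at all for those mothers. The fall-back is placed under follow-up, so the text does not establish this. Even for a baseline already taken that way, only observed change is missing. A model on raw waist values, or imputation, could still use the later measurements, although neither is specified for this case.
- A reader might infer that the loss follows site closures and so differs between arms. The stated trigger concerns one participant's home or one mother's travel. Data collection is otherwise the same in both arms (H2), and nothing links use of the route to arm. Clustering by site is possible, but an imbalance is not shown.

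**Conclusion.** The point holds in a limited form. As written, every follow-up visit done by the mailed-scale route loses that visit's waist and blood pressure values. Loss of observed change at both later visits follows only where the baseline was also taken that way. The text supports this for the initial months, if mothers were enrolled by those methods then, but does not settle it for later use.

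The number of mothers affected is unknown. For an assumed 10% to 30% loss, the standard error of the waist contrast rises by about 4% to 15% if the loss is spread over sites at ICC 0.05, and by about 5% to 20% if whole sites are lost. Smaller waist effects would have less margin, while an effect as large as the earlier trial's would still be well powered. Weight is still measured, so the primary analysis is not touched. This is a minor, worthwhile improvement and not a threat to the trial's main conclusion.

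**What to change.** In the fall-back paragraph of Appendix C, add a tape measure to the mailed parcel, and the automated cuff where stock allows. State that waist (and blood pressure, if a cuff is sent) is taken by the coached phone or video procedure already set out for baseline, at any visit that uses this route.

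The cost is a tape in a parcel already being sent, a few minutes of coaching at the follow-up contact that the fall-back already schedules, and one line of text. The appendix does not describe that contact in full, so the line should say that it takes place by phone or video.

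There are two limits. Self-measured waist is noisier than staff-measured waist, though the main COVID route already accepts self-measurement. Values already missed, including any early-pandemic baselines, cannot be recovered by this change.

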### **Intervention delivery**

Consistent with the D&I focus of the study, we will follow each site's practice regarding whether and how visits continue (e.g., virtual, phone, in person). Recognizing the dynamic nature of the situation, we will coordinate with PAT National Center regarding data they are collecting at the site level in terms of what types of visits are being offered as well as what site leaders and parent educators indicate. Parent educators also still have the option to complete visit records for visits conducted virtually with mom's

---

enrolled in the study. The visit record form now has an item to indicate how the visit was conducted (i.e., in person vs virtual (phone/video conference).

### **Additional challenges**

As we resume data collection at additional sites, and as sites who have not yet begun data collection start this process, we anticipate we may need to add additional options. We will communicate with sites about the process which will work best for them and if needed, request modifications accordingly.

